5.2. Inclusion – Exclusion Criteria and General Study Population

The general study population will include a total of at least 36 adult patients with pulmonary sarcoidosis, age 18 to 75 years, inclusive. The inclusion and exclusion criteria defined in the protocol apply to all patients regardless of age stratification and are not repeated herein the SAP. Reference is made to the final protocol for the specific inclusion and exclusion criteria for patients.

Patients withdrew for reasons other than treatment-related AEs may be replaced.

5.3. Randomization and Blinding

It is planned that 36 patients with pulmonary sarcoidosis will be randomized into one of 3 sequential cohorts, each comprising 12 patients allocated 2:1 (block size of 6) to ATYR1923:Placebo.

The master randomization schedule will be made of randomly permuted blocks of appropriate sizes, as determined by the unblinded study team member producing the schedule. The schedule will be generated electronically.

For patients who are replaced, the replacements should take the same treatment assignment as the original patient to ensure that the treatment groups stay balanced.

The randomization code will be produced within the interactive web response system (IWRS). The study center pharmacist will be provided access to the randomization code within the IWRS and through notifications generated by the IWRS. The laboratory where the PK samples are to be analyzed will also be provided access to distinguish between samples of patients dosed with ATYR1923 versus placebo.

Patients who withdraw for any reason without completing all screening evaluations successfully, will be considered “screen failures”.

Randomization will be performed using an IWRS. The patient will be issued a randomization number only after the patient has met all Inclusion and Exclusion criteria.

The following controls will be employed to maintain the double-blind status of the study:

- The infusion solution containing active drug and placebo will be indistinguishable in appearance.
- The study center pharmacist will have access to randomized treatment assignments via IWRS for dispensing purposes; treatment assignments will be accessible only to the pharmacist and authorized personnel and will be maintained in a blinded fashion.

aTyr Pharma, Inc.
Study ATYR1923-C-002 Statistical Analysis Plan
IND#: 133692

FINAL Version 1.0
2021-08-02

Rules for unblinding a patient for safety reasons are fully described in the Protocol and not repeated herein this SAP.

6. SAMPLE SIZE

For this study, no prospective calculations of statistical power have been made. The sample size has been selected to provide information on safety, tolerability, immunogenicity, PK and efficacy following single doses of ATYR1923. Any p-values to be calculated will be interpreted in the perspective of the explorative character of this study.

7. GENERAL CONSIDERATIONS

7.1. Analysis Sets

7.1.1. Safety Set

The Safety Set will comprise all patients who receive any amount of study drug and will be based on the actual treatment received, if this differs from that to which the patient was randomized.

7.1.2. Modified Intent-to-Treat Set (mITT)

The mITT Set will comprise all patients who have received any amount of study drug and will be based on the randomized treatment, regardless of which treatment the patient actually received.

7.1.3. Efficacy Evaluable Set (EE)

The EE Set includes all subjects who have received at least four doses of study drug and no major protocol deviations that may affect the interpretation of efficacy. Decisions regarding exclusion of patients from the EE Set will be documented before unblinding of the treatment assignments. Treatment groups will be analyzed based on the randomized treatment.

7.2. Covariates and Subgroups

7.2.1. Planned Covariates

There are no planned covariates for the primary analysis (i.e. for endpoints based on safety data). Specific covariates used for efficacy endpoints are described within the respective efficacy endpoint definitions elsewhere in this document.

7.2.2. Planned Subgroups

There are no planned subgroup analyses (i.e. for endpoints based on safety data). Specific subgroups used for efficacy endpoints are described within the respective efficacy endpoint definitions elsewhere in this document.

7.3. Management of Analysis Data

7.3.1. Baseline Definition

Unless otherwise specified, baseline measures are the last measures assessed on or before the first dose date. If multiple measures are taken on Day 1 (e.g., vital signs, 12-lead ECG), then the last measure before the first dose will be used as baseline.

Baseline OCS dose is defined as the dose recorded in the OCS log prescribed for the day before the first dose of the study drug.

7.3.2. Data Handling

Unscheduled or repeated laboratory (with the exception of coagulation) and clinical test results will not be analyzed in the summary of continuous values unless used as baseline data, but will be included in the laboratory or clinical shift tables as follows:

- Unscheduled/repeated tests will be included with the nearest regularly scheduled test. If there is a scheduled test and one or more unscheduled tests assigned to the same time point, the most conservative test (i.e., a test with low or high results) will be used.
- If it is not obvious which repeated/unscheduled result is more abnormal, then the results closest to the scheduled target day would be summarized in shift tables.

For Coagulation parameters, PT, PTT and INR, any repeated parameter will replace original scheduled visit values in the prior scheduled visit, for both change from baseline summaries, as well as shift tables.

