- Serum complement (CH50, C3, and C4) and tryptase.
- ATYR1923 serum concentrations.
- Jo-1 and ADA.

Additionally, the following tests and procedures are to be performed 1 to 2 hours after the onset of symptoms:

- Samples for assessment of:
- Complete safety laboratory panel, including urine analysis and urine microscopy.
- IgE.
- Plasma complement factors (C3a, C4a, C5a, Bb, SC5b-9).
- Serum complement (CH50, C3, and C4) and serum tryptase.

Serum biomarkers/cytokines.

The Investigator must inform the study Medical Monitor promptly regarding any patient who experiences a generalized IRR for additional instruction.

Patients who experience generalized IRRs will continue to be monitored / have repeat assessments performed at a schedule determined by the Investigator in consultation with the Medical Monitor and Sponsor. Appropriate follow up for the patient must occur to ensure that there are no late-occurring sequelae.

Note that in the eCRF, AEs that occur during or within 24 hours after study drug injection should be captured as individual signs and symptoms rather than a diagnosis of allergic reaction or IRR.

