9.2. Clinical Laboratory Evaluations

Clinical laboratory results will be summarized descriptively for each treatment group by timepoint for the observed value as well as for the change from baseline value. In addition, laboratory shift tables will be provided for all laboratory parameters where low/normal/high or abnormal/normal status can be ascertained. Listings of individual laboratory parameters by visit with normal ranges and abnormality assessments will also be provided.

In addition, since anticoagulation medication may affect coagulation parameters, each record will be examined by medical monitor. Coagulation parameters of Subjects with concomitant medications of warfarin sodium, apixaban, rivaroxaban between screening and end of treatment are excluded for all visits.

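### SAP 7.3.2 lets unscheduled non-coagulation laboratory results from about the first week after the first infusion attach to the pre-dose Day 1 visit, where a by-visit shift table has no post-baseline cell for them

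*SAP*

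**What the plan says.** **Assignment (SAP 7.3.2).** For shift tables, "Unscheduled/repeated tests will be included with the nearest regularly scheduled test". Where a scheduled and an unscheduled test share a time point, "the most conservative test (i.e., a test with low or high results) will be used". The section does not require the receiving visit to lie on the same side of the first dose as the result.

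**Scope (SAP 7.3.2).** "Unscheduled or repeated laboratory (with the exception of coagulation) and clinical test results will not be analyzed in the summary of continuous values", unless they serve as baseline. Coagulation follows its own rule: "any repeated parameter will replace original scheduled visit values in the prior scheduled visit". That rule governs the change-from-baseline summaries as well as the shift tables.

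**Baseline (SAP 7.3.1).** In general, "baseline measures are the last measures assessed on or before the first dose date". If several measures are taken on Day 1, "then the last measure before the first dose will be used as baseline".

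**Output (SAP 9.2).** "laboratory shift tables will be provided for all laboratory parameters where low/normal/high or abnormal/normal status can be ascertained". The section does not say whether the tables are by visit or show the worst post-baseline value.

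**Schedule (Protocol Table 1, repeated in the SAP).** Haematology, chemistry and urinalysis are taken at Screening and on Days 1, 15, 29, 57, 85, 113, 141 and 169. Coagulation is taken at Screening and then from Day 29, with nothing on Day 1 or Day 15. Dosing-day assessments are pre-dose unless stated otherwise.

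**Foreseen unscheduled samples.** Protocol 9.9 requires, 1 to 2 hours after the onset of infusion-reaction symptoms, a "Complete safety laboratory panel, including urine analysis and urine microscopy". Protocol 8.5.9 asks for prompt repeats of unexplained or unexpected values.

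**The concern.** A shift table compares baseline status with status after treatment. The Day 1 sample is taken before dosing and normally supplies the baseline. A result drawn after the first infusion belongs on the post-treatment side, but proximity alone can place it with Day 1. SAP 7.3.1 does not admit it as baseline, and SAP 7.3.2 gives it no later visit. It is left without a cell.

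The results at risk are those prompted by something happening soon after first exposure, such as an infusion reaction or an unexpected value that was rechecked. The same panel drawn after the Week 4 infusion would attach to Day 29, a post-baseline visit, and would count. Only the first infusion is treated differently. The two sections also leave room for different programmers to produce different tables from the same data.

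**Working it through.** The plan states no figure on this point, so there is none to reproduce. The check applies the written rule to the schedule.

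**1. Nearest scheduled test, haematology, chemistry and urinalysis.** A result on Day d goes to the scheduled day s with the smallest |d − s|. Between Day 1 and Week 2 the switch is at the midpoint, (1 + Week 2 day) / 2. The Week 2 window is ±2 days.

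| Week 2 visit on | Midpoint (tie) | Days after Day 1 that attach to Day 1 |
|---|---|---|
| Day 13 | (1 + 13)/2 = Day 7 | 2 to 6 |
| Day 15 (nominal) | (1 + 15)/2 = Day 8 | 2 to 7 |
| Day 17 | (1 + 17)/2 = Day 9 | 2 to 8 |

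A post-infusion sample on Day 1 itself is at distance 0 and also attaches to Day 1. This covers the post-reaction panel at the first dose. SAP 7.3.2 has no rule for a result equidistant from two visits; its second bullet only chooses between results already at one visit.

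**2. What the shift table then shows.** Take an illustrative ALT that is normal pre-dose, high on Day 5 and normal on Day 15. The distances are |5 − 1| = 4 and |5 − 15| = 10, so the Day 5 value attaches to Day 1.

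- *SAP 7.3.1 respected:* baseline stays normal. The high value sits at a visit with no post-baseline cell. Week 2 shows Normal to Normal, and the high value is absent from a by-visit table.
- *Most-abnormal-result rule allowed to override SAP 7.3.1:* the high value replaces the Day 1 value, and the table shows High to Normal.
- *Assignment limited to post-baseline visits:* Week 2 holds a high and a normal result, the more abnormal is used, and the table shows Normal to High.

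The first follows from reading the two sections together. The second requires disregarding SAP 7.3.1.

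**3. Coagulation.** The nearest-test rule does not apply. With no scheduled test on Day 1 or Day 15, the scheduled visit before any repeat on Days 2 to 28 is Screening. With the ±3-day Week 4 window, the last such day ranges from Day 25 to Day 31. Screening is normally the coagulation baseline, so the replacement rule would overwrite a pre-dose baseline with a post-dose value, contrary to SAP 7.3.1.

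**4. Size per patient.** Each dose cohort plans 8 active patients, so one missing shift is 1/8 = 12.5% of a dose arm in that table. The documents give no basis for estimating how many results would be affected.

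**The case against.** The strongest reply is that little is lost.

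- **The results are reported elsewhere.** All collected data are listed, and SAP 9.2 lists laboratory values with normal ranges and abnormality assessments. Protocol 8.5.9 sends clinically significant deviations to the adverse-event record, so they reach the adverse-event tables. SAP 9.1 also tabulates suspected infusion-related events. Protocol 10.1.2.3.2 promises a summary of out-of-range laboratory data. This stands and limits the harm, but it does not make the shift table correct. Listings do not compare arms. Protocol 9.1.1 generally keeps abnormal findings without clinical significance out of the adverse-event record. SAP 9.2 does not separately set out the out-of-range summary.
- **The layout is unknown.** SAP 9.2 does not specify by-visit tables, so the omission is an inference from the literal rule. That is fair, and the conclusion is conditional on it.
- **The gap is narrow.** It concerns the first of six infusions and needs an unscheduled draw, because the only planned contact between Days 1 and 15 is by telephone. This also stands.

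A reader might infer more than the documents support:

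- *That every laboratory result is affected in this way.* Coagulation is expressly excepted and has a different problem.
- *That first-week abnormalities will appear as improvement, High to Normal.* SAP 7.3.1 bars a post-dose value from being baseline when the pre-dose sample exists, so this arises only if that section is overridden.
- *That ECG results up to about Day 14 are lost in the same way.* SAP 9.4 plans values and changes by time point and names no ECG shift table.
- *That the primary analysis is compromised.* The primary endpoint is the incidence of TEAEs and SAEs, which does not use the shift tables.

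**Conclusion.** The defect is real and small. As written, SAP 7.3.2 attaches unscheduled haematology, chemistry and urinalysis results from after the first infusion through about Day 7 to a pre-dose visit. The last such day is Day 6, 7 or 8 depending on when Week 2 falls, with an unresolved tie on the following day. Read with SAP 7.3.1, these results drop out of a by-visit shift table.

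This assumes that the shift tables are by visit, that the scheduled pre-dose Day 1 sample was taken, and that the nearest-test rule is programmed literally. For non-coagulation tests the consequence stays within the shift tables. The coagulation rule carries a parallel gap before Week 4, which by its own terms also reaches the change-from-baseline summaries. The frequency of such results is unknown. This is a minor correction.

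**What to change.** Add to SAP 7.3.2:

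1. Any result obtained after the start of the first infusion is assigned to the nearest post-baseline scheduled visit. Screening and Day 1 accept pre-dose results only.
2. A rule for ties. Closing Day 1 to post-dose results removes the Day 8 tie, but ties between later visits remain, for example Day 22 = (15 + 29)/2 and Day 43 = (29 + 57)/2. Say also whether distance is measured to the actual or the target visit day.
3. The same limit for coagulation: a post-dose repeat may not replace a Screening value. Because no post-baseline coagulation visit precedes Week 4, state where an earlier repeat goes and that it does not displace the scheduled Week 4 value by default.

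A baseline-to-worst-post-baseline column in each shift table is optional. It would make the display less dependent on visit assignment, but its absence is not an error.

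The cost is a few sentences in the SAP and the matching change to the programming specification. No new data are needed.

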7.3.3. Missing Data

In general, missing data will not be imputed, unless methods for handling missing data are specified. All study related data that is collected will be included in data listings that will accompany the clinical study report.

7.3.3.1. Missing Date Values

The following conventions will be used to impute missing portions of dates for adverse events and concomitant medications, if warranted. Note that the imputed values outlined here may

not always provide the most conservative date. In those circumstances, the imputed value may be replaced by a date that will lead to a more conservative analysis.

A. Start Dates

- 1) If the year is unknown, then the date will not be imputed and will be assigned a missing value.
- 2) If the month is unknown, then:
 - i) If the year matches the first dose date year, then impute the month and day of the first dose date.
 - ii) Otherwise, assign 'January.'
- 3) If the day is unknown, then:
 - i) If the month and year match the first dose date month and year, then impute the day of the first dose date.
 - ii) Otherwise, assign the first day of the month.

B. Stop Dates

- 1) If the year is unknown, then the date will not be imputed and will be assigned a missing value.
- 2) If the month is unknown, then assign 'December.'
- 3) If the day is unknown, then assign the last day of the month.

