8.5.7. Adverse Events

AEs will be recorded from the time of written informed consent through the last visit for a patient. Any clinically significant observations in results of clinical laboratory, 12-lead ECGs, vital signs, pulse oximetry, or physical examinations are to be recorded as part of the patient's medical history if occurring prior to start of dosing and as an AE if occurring after the start of study drug administration at Day 1, where the finding represents a change from Baseline.

A TEAE is defined as any event not present prior to (the first) administration of the study drug or any event already present that worsens in either intensity or frequency following exposure to the study drug.

An AE which occurs prior to (the first) administration of the study drug will be considered a pre-treatment AE.

AEs that occur during or within 24 hours after study drug injection should be captured as individual signs and symptoms (eg, dyspnea, rash, flushing) rather than a diagnosis of allergic reaction or IRR.

At study visits, patients will be asked non-leading questions to determine the occurrence of AEs. Patients will be asked in general terms about any AEs at regular intervals during the study. In addition, all AEs reported spontaneously during the course of the study will be recorded.

The intensity of each AE will be rated by the Investigator using the National Cancer Institute Common Terminology Criteria for Adverse Events (NCI CTCAE), version 5.0 (available

at: https://ctep.cancer.gov/protocolDevelopment/electronic_applications/docs/CTCAE_v 5_Quick_Reference_8.5x11.pdf).

AEs not listed on the NCI CTCAE are to be rated by the Investigator as "mild (Grade 1)", "moderate (Grade 2)", "severe" (Grade 3), "life-threatening" (Grade 4), or "fatal" (Grade 5).

The relationship between the AEs and the study drug will be indicated as "not related", "unlikely related", "possibly related", or "related". AEs assessed as "possibly related" or "related" will be considered to be related to the study drug whereas AEs assessed as "not related" or "unlikely related" will be considered not to be related to the study drug.

Details on the rating of the severity of the AEs and relationship to the study treatment are given in Section 9.2.

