8.5. Prior and Concomitant Medications

The number and percentages of concomitant medications and prior medications that are ongoing at the start of study drug will be summarized by Anatomical Therapeutic Chemical (ATC) level 2 and PT. The total number of prior/concomitant medications and the number and percentages of patients with at least 1 medication will be summarized. All summaries will be performed using the Safety Set. Similarly, non-OCS sarcoidosis medications will be summarized separately.

A listing will present all prior and concomitant medications. Non-OCS sarcoidosis medications will be presented in a separate listing.

A concomitant medication is defined as any medication taken on or after the day of first exposure to study drug up until 30 days after last dose of study drug.

A Prior medication is defined as any medication that the patient is started and stopped prior to the day of first exposure to study drug, collected from up to 30 days prior to Screening.

If a medication has a missing start date, then it is conservatively assumed to be both prior and concomitant only.

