9.1. Adverse Events

Adverse events will be coded using the Medical Dictionary for Regulatory Activities (MedDRA), version 24.0. Adverse events will be recorded from the date of informed consent, throughout the clinical trial.

Treatment-emergent adverse events (TEAEs) are defined as any adverse event or worsening of an existing condition after initiation of the investigational product and through 30 days after the patient's last study visit (study completion or early termination).

If the onset of an AE is on Day 1, then the time of first dose, collected from the Study Drug Administration CRF, will be compared to the time of onset to determine if the AE is treatment-emergent. If the start time is reported as "unknown", the AE is classified as TEAE.

The number and percent of patients with any TEAEs as well as number of TEAEs will be summarized by system organ class and preferred term by treatment and overall. At each level of tabulation (ex. at the preferred term level) patients will be counted only once if they had more than one such event reported during the AE collection period.

Level of intensity will be assessed using the CTCAE grading.

The following summary tables and patient level listings will be presented for AE data:

- Overall summary of TEAEs, including the number and percentage of the following: any TEAEs, treatment-related TEAEs, Serious TEAEs, TEAEs leading to study drug withdrawal, leading to study drug interruption, TEAEs leading to deaths, Grade 3 or 4 TEAEs, TEAEs suspected to be infusion related;
- Summary table of TEAEs by SOC and PT;
- Summary table of TEAEs by PT;

- Summary table of TEAEs by highest relationship level to study drug by SOC and PT;
- Summary table of TEAEs by maximum intensity by SOC and PT;
- Summary table of serious TEAEs by SOC and PT;
- Summary table of suspected infusion related TEAEs by SOC and PT;
- Listing of suspected infusion related TEAEs;
- Listing of all Non-Treatment-Emergent AEs;
- Listing of all TEAEs;
- Listing of AEs leading to study drug interruption;
- Listing of AEs leading to study drug withdrawal;
- Listing of AEs leading to death;
- Listing of TEAEs of grade 3 or 4;
- Listing of Serious TEAEs.

In summary tables, missing data are imputed per rules established in Section 7.3.3.1.

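### The SAP's partial-date rule ignores the stop date, so read literally it can count an adverse event that ended before first dose as treatment-emergent

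*SAP*

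**What the plan says.** SAP 7.3.3.1 (Missing Date Values) covers partial dates for adverse events and concomitant medications. Two start-date rules matter here:

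- Rule A.2(i), month unknown: "If the year matches the first dose date year, then impute the month and day of the first dose date".
- Rule A.3(i), day unknown: "If the month and year match the first dose date month and year, then impute the day of the first dose date".

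The stop-date rules fill in only what is missing, for example "If the day is unknown, then assign the last day of the month". A complete stop date stays as recorded. No rule compares the start with the stop.

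Two qualifiers apply. Imputation is to be done where warranted, a term the SAP does not define. The section also concedes that an imputed date may not be the most conservative one, and adds: "In those circumstances, the imputed value may be replaced by a date that will lead to a more conservative analysis".

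SAP 9.1 (Adverse Events) defines a TEAE as an event, or a worsening, that follows the start of study drug. For an onset on Day 1, the onset time is compared with the time of first dose, and if the onset time is unknown "the AE is classified as TEAE". The section ends: "In summary tables, missing data are imputed per rules established in Section 7.3.3.1".

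Protocol 8.5.7 records AEs from informed consent and states: "An AE which occurs prior to (the first) administration of the study drug will be considered a pre-treatment AE". SAP 4.2.1 makes the incidence of TEAEs and SAEs the primary endpoint.

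**The concern.** Moving an uncertain onset to the first-dose date is a normal convention when it is unclear whether an event began before or after dosing. It gives the wrong answer when the stop date already settles the question. An AE that is known to have ended before first dose cannot be treatment-emergent, whatever its exact onset.

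Because AEs are collected from consent, events that begin and resolve during screening will be in the AE data, and SAP 9.1 plans a listing of non-treatment-emergent AEs. For those with a partial onset, the rules as written can produce a start later than the stop and place the event in the TEAE tables. At stake is the accuracy of the primary safety summary in arms of 8 to 24 patients, and the internal consistency of the dates behind it.

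**Working it through.** The plan states no figure on this point, so the check applies the rules literally to test dates and then sizes one misclassification.

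**1. Inputs**

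- Start and stop rules: SAP 7.3.3.1.
- Day 1 rule and use of the imputed dates: SAP 9.1.
- Pre-dose window: up to 28 days (protocol 4.1.1), or 6 weeks (42 days) under the COVID-19 provision (protocol 6.3.1).
- Planned arm sizes: 8 active and 4 placebo in each of 3 cohorts (SAP 5.1), so 3 × 8 = 24 active and 3 × 4 = 12 placebo.
- Assumed for illustration: first dose on 20 March 2020, and unknown onset time whenever the onset date is partial.

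**2. Rules as written**

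| Case | Recorded start | Recorded stop | Start used | Stop used | Class | Start after stop? |
|---|---|---|---|---|---|---|
| a | Mar 2020, day unknown | 12 Mar | 20 Mar | 12 Mar | TEAE | Yes |
| b | 2020, month unknown | 12 Mar | 20 Mar | 12 Mar | TEAE | Yes |
| c | 2020, month unknown | Feb 2020, day unknown | 20 Mar | 29 Feb | TEAE | Yes |
| d | Feb 2020, day unknown | 12 Mar | 1 Feb | 12 Mar | Not TEAE | No |
| e | Mar 2020, day unknown | Mar 2020, day unknown | 20 Mar | 31 Mar | TEAE | No |
| f | 8 Mar | 12 Mar | 8 Mar | 12 Mar | Not TEAE | No |

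Cases a to c are wrong: the known part of the stop date puts the end of the event before dosing. Case e is a reasonable cautious call, because there the stop is not known to precede dosing.

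**3. With a stop-date condition**

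If the stop shows that the event ended before first dose, take the earliest start consistent with the known parts and class the event as non-treatment-emergent. Case a then starts on 1 March, and cases b and c on 1 January. All three leave the TEAE count and none is inverted. Cases d to f do not change.

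**4. Size of one misclassification**

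SAP 9.1 counts each patient once at each level of tabulation. One wrongly counted patient therefore moves a row only if that patient has no other event in it:

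- one active arm: 1/8 = 12.5 percentage points
- combined placebo: 1/12 = 8.3 points
- combined active: 1/24 = 4.2 points

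**5. How much of screening the rules reach**

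For a first dose on day d of a month, min(d − 1, 28) of the preceding 28 days fall in the same month. Summed over a 365-day year:

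- 31-day month: 406 + 2 × 28 = 462
- 30-day month: 406 + 28 = 434
- February: 378
- Same month: (7 × 462 + 4 × 434 + 378) / (365 × 28) = 5,348 / 10,220 = 52%
- Same year: (406 + 336 × 28) / 10,220 = 9,814 / 10,220 = 96%

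For a 42-day window:

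- Same month: (7 × 465 + 4 × 435 + 378) / (365 × 42) = 5,373 / 15,330 = 35%
- Same year: (903 + 322 × 42) / 15,330 = 14,427 / 15,330 = 94%

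These are calendar shares: the part of screening in which a partial onset would meet rule A.3(i) or A.2(i). They are not error rates. The documents do not say how many AE dates will be partial, so the number of affected events cannot be calculated.

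**The case against.** The best defence is that the SAP already leaves room for the right answer. If a stop date precedes dosing, no imputation is needed to classify the event, so a programmer could decide that it is not warranted. The TEAE definition in SAP 9.1 and the pre-treatment category in protocol 8.5.7 also point the right way. All this is true, but none of it prescribes the correction. The qualifier is undefined, the replacement by another date is optional, and for a safety count the conservative direction is normally to keep the event as a TEAE.

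The second defence is rarity, and it largely stands. Protocol 9.3 requires onset and resolution date and time for every AE, and protocol 12.2 asks for an explanation of all missing data. Protocol 8.5.7 sends clinically significant pre-dose test and examination findings to medical history. An onset month that is unknown for an event arising within weeks of consent is unusual, so the day-unknown rule is the practical case. The study is also descriptive, with no formal hypothesis testing (SAP 7.4.1), so no error rate or power is affected.

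A reader might infer more than the text supports, in three ways:

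- *That the rule turns a drug stopped before Day 1 into a concomitant medication.* SAP 8.5 defines concomitant use as use on or after the day of first exposure, and a drug with an earlier recorded stop was not so used. The prior definition reads: "A Prior medication is defined as any medication that the patient is started and stopped prior to the day of first exposure". At most, an imputed Day 1 start makes the drug fail that definition, and the same date check resolves it.
- *That AEs with an unknown onset year are lost.* Rule A.1 leaves them undated and SAP 9.1 sets no default. But AEs are collected only from consent and participation is planned for up to 28 weeks, so an unknown year is barely plausible. SAP 7.3.3 puts all collected data in listings.
- *That half or more of screening events would be misclassified.* The calendar shares above do not say this.

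**Conclusion.** The concern holds as a gap in a stated rule. Taken literally, SAP 7.3.3.1 with SAP 9.1 counts an AE known to have ended before first dose as a TEAE and gives it a start after its stop. That conflicts with the definitions the imputation is meant to serve.

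The likely count is small, and any error adds TEAEs rather than hiding them. The shifts of 4.2 to 12.5 points rest on the planned arm sizes and on the patient having no other event in that row. That condition is easier to meet in a row for a single preferred term than in the row for any TEAE. The conclusion also assumes that the qualifiers in SAP 7.3.3.1 are not used to override the rule. It is worth correcting because it touches the primary endpoint and costs almost nothing, not because it threatens the study's conclusions.

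**What to change.** Add to rules A.2(i) and A.3(i) of SAP 7.3.3.1:

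> ... unless the stop date (complete, or as far as it is known) shows that the event ended before the first dose date. In that case impute the earliest date consistent with the known parts, and class the AE as non-treatment-emergent.

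Add as a general condition, for AEs and medications alike:

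> An imputed start may not be after the stop date.

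Optionally, state a default for an AE with an unknown onset year, for example that it is a TEAE unless its stop date precedes first dose.

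The cost is a few lines of SAP text and of date-derivation code. No data collection changes. The change should be documented before treatment codes are released.
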